4.2 Study Endpoints for Stage I

4.2.1 Primary Study Endpoints

At approximately day 30 from randomization, a binary composite endpoint of venous and arterial thrombotic complications—including new, symptomatic proximal, or distal DVT of the upper or lower extremities, PE, and new thrombosis of other veins (including cerebral sinus and splanchnic veins), ischemic stroke, myocardial infarction, other arterial thromboembolism (e.g., mesenteric or acute limb ischemia), and all-cause mortality will be the primary study endpoint.

4.2.2 Key Secondary and Exploratory Endpoints

Key secondary endpoints include the following.

1. The composite endpoint for the primary outcome at day 45 following randomization
2. The composite endpoint for the primary outcome at day 90 following randomization
3. Composite endpoint of venous thromboembolic events, including symptomatic DVT of the upper or lower extremities, symptomatic and/or clinically relevant PE, and other symptomatic venous thrombosis, including cerebral sinus and splanchnic vein thrombosis at day 30
4. Composite endpoint of arterial thromboembolic events, including symptomatic ischemic stroke, myocardial infarction, and other symptomatic arterial thromboembolic events at day 30

Secondary endpoints will be formally tested using a fallback approach only if the primary endpoint was statistically significant at the two-sided 5% level.

Exploratory endpoints include the following.

1. All-cause mortality at day 30 following discharge from the hospital
2. All-cause re-hospitalization at day 90 following discharge from the hospital

4.2.3 Safety Endpoints for Stage 1

Safety endpoints will include (1) major bleeding, as defined by the ISTH, and (2) clinically-relevant, non-major bleeding, also as defined by the ISTH. Criteria for major bleeding, and for CRNMB are provided below

1. Major bleeding
 - a. Fatal bleeding
 - b. Bleeding into a critical area or organ (e.g., intracranial, intraspinal, intraocular, pericardial, intra-articular, intramuscular with compartment syndrome, retroperitoneal)
 - c. Bleeding causing a fall in the hemoglobin level of 2 g/dL or more, or leading to transfusion of 2 or more units of whole blood or red cells
2. Clinically-relevant, non-major bleeding
 - a. Bleeding requiring medical intervention by a healthcare professional
 - b. Bleeding leading to hospitalization or an increase in the level of care
 - c. Bleeding prompting a face-to-face (i.e., not just a telephone or electronic communication) evaluation

4.2.4 Adjudication of outcome events

All patient-reported events will be investigated by the Clinical Coordinating Center, including obtaining information from healthcare facilities where the patient received treatment. An

independent, central adjudication committee (ICAC) will review and adjudicate events in a blinded manner without knowledge of treatment allocation. During the study period, the ICAC will adjudicate all suspected occurrences of venous or arterial thromboembolic events, ischemic stroke, acute myocardial infarction, deaths, and re-hospitalization. The ICAC will also review all suspected episodes of bleeding that require medical attention and categorize adjudicated bleeding as major, clinically-relevant non-major, or minor bleeding. The Committee will be provided with all relevant documentation related to the events. The criteria and definitions of the study outcomes, as well as the procedures followed by the Committee, will be described in an adjudication manual which will be provided to the ICAC members prior to the first meeting.

5. Study Enrollment

5.1 Inclusion Criteria

The inclusion criteria for Stage 1 of this adaptive protocol are listed below and in Appendix 3.

Potential study participants will be identified during hospitalization and reviewed for inclusion/exclusion criteria. Per the adaptive trial design strategy, these criteria may change after the first and subsequent analyses of in-trial accrued data.

- Age \geq 18 years
- COVID-19 positive test (PCR, antigen, or point of care test diagnosing a current infection) within 2 weeks of hospital admit date
- Hospitalized for COVID-19 infection for 48 or more hours

5.2 Exclusion Criteria

The exclusion criteria for Stage 1 of this adaptive protocol are listed below and, with additional details, in Appendix 3. These are potentially subject to change based on the adaptive trial design and analyses of in-trial accrued data.

- Existing indication for anticoagulation, either therapeutic or prophylactic dose
- Contraindication to antithrombotic therapy, such as
 - Ischemic stroke, intracranial bleed, or neurosurgery within 3 months
 - Known bleeding within the last 30 days requiring emergency room presentation or hospitalization
 - Known major surgery within 14 days (at least 1 hour and/or requires general anesthesia)
 - Inherited or active acquired bleeding disorder
- Platelet count $< 50,000/\text{mCL}$
- Hemoglobin $< 8 \text{ gm/dL}$
- Pregnancy
- Prison inmate
- Life expectancy less than 90 days
- Unwilling or unable to provide informed consent / unwilling or unable to complete the study protocol
- Other criteria related to stage-specific appendices developed as adaptations to the trial. (i.e. Stage 1 is in appendix 3)

5.3 Vulnerable Subjects

As noted in the Exclusion Criteria, this study will not enroll children < 18 years of age, pregnant women, or prisoners.

5.4 Strategies for Recruitment and Retention

The Protocol Implementation Committee (PIC) will respond to the evolving landscape of the pandemic by leveraging the network of networks already established within ACTIV-4, including all sites participating within the networks. As is currently evident, the pace of the pandemic varies across different areas within the United States, based on propagation patterns, local social distancing rules, and compliance with those rules. In addition, the PIC will also be monitoring the course of the pandemic across the world to identify regions where the number of potential study subjects would make rapid recruitment feasible. By monitoring the evolution of the infection, the PIC will place sites on hold when disease activity wanes in their geographic areas and activate new sites when the local rate of new COVID-19 cases exceeds a threshold making recruitment feasible.

Screening and enrollment will occur within the hospital setting, targeting patients being considered for discharge within 72 hours. Providers managing these patients will be made aware of the study, and the research team at each site will review the list of inpatients to identify potentially eligible patients for the study. Study participants will be provided with study drug at the time of discharge from the hospital, with detailed instructions for taking the medication. At those sites with the capability to process and store biospecimens, those patients who agree to participate will be asked to provide samples for preparation of plasma, serum, and genomic DNA, as described below.

The local study team will collect relevant contact information for the participant, participant's spouse or partner, one contact individual who is not related to the participant to maintain contact, and the participant's Primary Care Physician. The local study team will inform the participant about the Call Center's role and, if possible, put the phone number in the participant's phone so they recognize the caller later. The participant will be asked to sign a Release of Records form for the PCP or other hospital. This form will have an expiration date 150 days after randomization.

One encounter with the study participant will occur at one to three days after discharge, to confirm medication compliance and collect information concerning any early outcome events. Five additional encounters for confirming compliance with the protocol and collecting outcome information will occur at 10 days, 20 days, 30 days, 45 days, and 90 days from initiation of the study. These visits may be set up to be electronic only (e-mail or text) or by telephone, depending on which approach works best for the individual study participant. The study is completed within approximately 90 days of hospital discharge.

Site investigators will be educated about the importance of retention of subjects in the study and will be informed about the steps that will be taken to prevent missing data. Study participants will be educated about the importance of their completion of the study and the different options available for them to accomplish this objective. Study participants who discontinue treatment with the study medication will continue to be followed by the study team unless the participant requests to be withdrawn from the study. Regular web-based and/or phone-based contacts during the course of study participation are designed to maintain ongoing interaction and support retention in the study.

Enrollment and retention of economically-disadvantaged individuals. The overall success of this study is critically dependent on the ability of all patients who meet inclusion/exclusion criteria to participate in the study. Populations historically affected by health disparities, including non-Hispanic Blacks and Hispanics, have been shown in several studies to be disproportionately affected by and hospitalized with COVID-19 (25, 26). These populations are also disproportionately affected by economic disparities, which can lead to difficulties with obtaining costly outpatient medications, leading to non-compliance. Consequently, the first stage of this study will provide the anticoagulant and the matching placebo to eliminate this potential reason for not participating in the study. This

approach will ensure that this study is relevant to the entire range of patients hospitalized with COVID-19.

5.5 Duration of Study Participation

Study participation lasts from the time the participant is enrolled into the study until 90 days from hospital discharge.

Total Number of Participants

Sample size calculations for Stage 1 are described in Section 7. Initial power calculations using conservative event rates from post-hospital extended duration VTE prophylaxis trials in medically ill patients selected for increased risk suggest that 2,660 participants per arm will be required to determine if thromboprophylaxis with an anticoagulant is superior to no anticoagulant thromboprophylaxis. There will be interim monitoring to enable early stopping for futility, efficacy, or safety.

5.6 Participant Withdrawal or Termination

5.6.1 Reasons for Withdrawal or Termination

Study participants are free to withdraw from participation in the study at any time upon written request. The site PI will notify the Clinical Coordinating Center of all withdrawals from the study. Study participants who withdraw consent will not have additional information collected after they withdraw from the study.

A site investigator may discontinue study drug for a study participant on the basis of either:

- Any clinical adverse event, laboratory abnormality, or other medical condition or situation occurs such that continued study drug treatment would not be in the best interest of the patient.
- The participant meets an exclusion criterion, either newly developed or not previously recognized (e.g., new thrombocytopenia, renal insufficiency), that precludes further study medication continuation.

Study participants may choose to withdraw from participation in the study at any time.

As noted above, study participants who discontinue taking the study drug prior to completing 30 days of therapy will continue to be followed as study participants, unless they also request to be withdrawn from the study.

5.6.2 Premature Termination or Suspension of Study

All deaths, SAEs, and related clinical events within the study period will be reviewed by the DSMB. The decision to stop or suspend the study will be made by the DSMB after considering the totality of the data and the benefit-risk of continuing the study. These decisions could lead to an adaptive change in the protocol, with one arm of the study being discontinued or modified/changed to an alternative approach.

The study may resume once concerns about safety, protocol compliance, and data quality are addressed and satisfy the IRB, the DSMB, and the sponsor.

5.7 *Study Agents*

Study agents for Stage 1 (described in more detail in Appendix 3) include:

- 1) Prophylactic anticoagulant, defined as a dose intended for the prevention of VTE; and
- 2) Matching placebo

Subsequent adaptations of this study may focus on modifications to the antithrombotic strategy, specific subsets of patients identified as being higher-risk for thrombotic complications, or other changes, as outlined in Figure 1.

5.8 Duration of Therapy

Duration of the thromboprophylaxis period will be 30 days, beginning at the time of discharge from the hospital. Primary outcome will be assessed by approximately 30 days after randomization.

Study participants will be followed for an additional 60 days after discontinuation of thromboprophylaxis (total duration of study participation = approximately 90 days).

Study agents for subsequent stages will be determined based on the adaptive design of the trial.

6. Study Procedures and Schedule

6.1 Study Schedule

| | | | | | | | | | |
|--|--|--|---|--|--|--|--|----|--|
| Biorepository samples (substudy, optional) | | | X | | | | | X* | |
|--|--|--|---|--|--|--|--|----|--|

***Second biorepository sample should be collected between Days 30 and 45, after the patient has discontinued study drug.**

6.2 Laboratory Procedures/Evaluations

All study participants will have either (1) clinical/standard of care D-dimer results or (2) a study D-dimer drawn within 72 hours prior to randomization. Hgb, Creatinine, and Platelet Count can be within 72 hours prior to study enrollment. The creatinine is used in the calculation of the eGFR, and a eGFR <30 mL/min/1.73 m² is an exclusion criterion (see Stage 1 exclusion criteria in Appendix 3). Include the LFT, LDH and Albumin if completed during the participant's hospital stay. These results (LFT, LDH, and Albumin) can be the most recent if not drawn within 72-hour of hospital discharge.

In addition, participants who consent to the biorepository substudy will be given the option of providing a blood sample by phlebotomy or independently mailing in a dry blood spot sample at two time points:

- 1) On Day 0, prior to initiation of the study drug
- 2) Between Days 30 and 45, after the patient has discontinued the study drug.

The proposed samples to be collected for the biorepository during Stage 1 of the study are reviewed in Appendix 4. Samples collected for the biorepository may change to accommodate the adaptive design of the study in response to changes in trial design.

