2.2 Randomization

Randomization will be performed for study participants as close to the time of hospital discharge as possible. Hospitalized patients may be screened and approached about the study up to 72 hours prior to hospital discharge, but final enrollment and randomization should occur as close to the time

of discharge as possible. In Stage 1, participants will be randomized in a 1:1 ratio using an online randomization system to either Arm A (apixaban 2.5 mg twice daily); or Arm B (matching placebo). The randomization scheme will be determined by the study phase and its associated group of intervention arms. Randomization for Stage 1 will be stratified by (1) concomitant use of a single antiplatelet agent (yes/no), and (2) a maximal score of 5 or greater vs. a score of less than 5 by the WHO Ordinal Index (Table 3).

Table 3. WHO ordinal scale for clinical improvement (https://www.who.int/blueprint/priority-diseases/key-action/COVID-19_Treatment_Trial_Design_Master_Protocol_synopsis_Final_18022020.pdf)

| Patient State | Score | Descriptor |
|------------------------------|-------|--|
| Uninfected | 0 | No clinical or virological evidence of infection |
| Ambulatory | 1 | No limitation of activities |
| | 2 | Symptomatic: Limitation of activities |
| Hospitalized: Mild disease | 3 | Hospitalized; no oxygen therapy |
| | 4 | Hospitalized; oxygen by mask or nasal prongs* |
| Hospitalized: Severe disease | 5 | *Non-invasive ventilation or high-flow oxygen |
| | 6 | Intubation & Mechanical ventilation |
| | 7 | Ventilation and additional organ support – pressors, RRT, ECMO |
| Death | 8 | Death |

*chronic CPAP or BiPAP use for sleep apnea excluded

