The initial follow-up encounter, which will be conducted by the Call Center via the participant's preferred method (electronic or phone call), will occur within 2 days following discharge from the hospital, to confirm study medication adherence and perform an initial assessment of outcomes. Subsequent encounters, which will also be conducted by the Call Center electronically or by phone, will occur at 10, 20, and 30 days after enrollment. With each encounter, assessments of medication adherence and outcomes will be performed. Two additional encounters will occur after completion of the primary outcome, at 45 and 90 days after enrollment, to determine if there is an increased risk for thromboembolic complications following hospital discharge that extends for a longer period of time than 30 days and to facilitate/confirm collection of the 2nd set of biorepository specimens. All contacts will be scripted to ensure that all information is uniformly collected.

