6.2.1 Study encounters

Baseline screening and enrollment (occurs ~Day -3 up to Day 0)

1. Inclusion/exclusion criteria reviewed—including a pregnancy test, if necessary—and eligibility for the trial determined. Prior urine or serum pregnancy test results accepted as long as they are obtained within the hospitalization. Abstinence does not count as a reason not to obtain a pregnancy test.
2. Patient enrolled into the study and informed consent obtained
3. Patient provided with information concerning the study, contact information, etc.
4. Occurs during last few days of hospitalization

Encounter 1: Randomization (Day 0)

1. Patient randomized to study drug
2. Information concerning the study, contact information, etc., reviewed with the patient
3. Clinical/standard of care D-dimer results or a study D-dimer drawn within 72 hours prior to randomization
4. Randomization expected to occur on day of discharge from the hospital

Encounter 2: First follow-up (Day 2)

1. First post-discharge encounter
2. Confirm taking study medication, review for any outcome events, adverse events

Encounter 3: Day 10

1. Second post-discharge encounter
2. Confirm taking study medication, review for any outcome events, adverse events

Encounter 4: Day 20

1. Third post-discharge encounter
2. Confirm taking study medication, review for any outcome events, adverse events

Encounter 5: Day 30

1. Fourth post-discharge encounter
2. Confirm taking study medication, review for any outcome events, adverse events
3. Participant will stop taking the study medication on Day 30
4. Events occurring up to this encounter will be included in the primary outcome
5. Make and confirm arrangements for second biorepository encounter

Encounter 6: Day 45

1. Fifth post-discharge encounter
2. Review for any outcome events, adverse events
3. Confirm second biorepository encounter has occurred

Encounter 7: Day 90 encounter

1. Sixth and last post-discharge check-in
2. Review for any outcome events, adverse events
3. Follow-up ends after the Day 90 encounter

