### 3.6 RANDOMIZATION SCHEME

Randomization will be performed for study participants as close to the time of hospital discharge as possible. Hospitalized patients may be screened and approached about the study up to 48 hours before hospital discharge, but final enrollment and randomization should occur as close to the time of discharge as possible. Participants will be randomized in a 1:1 ratio using an online randomization system to either Arm A (apixaban 2.5 mg twice daily), or Arm B (matching placebo). Randomization will be stratified by (1) concomitant use of a single antiplatelet agent (yes/no), and (2) a maximal score of 5 or greater vs. a score of less than 5 by the World Health Organization (WHO) Ordinal Index.

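### Hemoglobin, creatinine and platelet results that decide three exclusions are dated from enrollment, so they may be up to about 144 h old at randomization if enrollment precedes Day 0

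*Protocol*

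**What the plan says.** Protocol Section 6.2 (Laboratory Procedures/Evaluations) sets the window for the three eligibility tests: "Hgb, Creatinine, and Platelet Count can be within 72 hours prior to study enrollment". The sentence before it dates a study D-dimer from randomization, also with a 72 h limit. Appendix 3 (A3.2.2) excludes patients on platelets (criterion 3), hemoglobin (4) and eGFR (5); Section 6.2 says that creatinine feeds the eGFR. D-dimer decides no exclusion.

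The timing of enrollment is described in several places:

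- **Section 6.2.1** opens with a baseline step, "Baseline screening and enrollment (occurs ~Day -3 up to Day 0", which includes "Patient enrolled into the study and informed consent obtained". Randomization is a separate Encounter 1 on Day 0: "Randomization expected to occur on day of discharge from the hospital".
- **Section 2.2** says "Hospitalized patients may be screened and approached about the study up to 72 hours prior to hospital discharge", but adds that "final enrollment and randomization should occur as close to the time" of discharge as possible.
- **SAP Section 3.6** gives a shorter approach window: "Hospitalized patients may be screened and approached about the study up to 48 hours before hospital discharge".
- **Section 4.1** counts follow-up from enrollment: contacts "will occur at 10, 20, and 30 days after enrollment".
- **Appendix 4** takes the first biospecimens at enrollment, and Section 6.2 puts that sample on Day 0.
- **Section 8.1** randomizes at the baseline visit.

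**The concern.** The tests that control entry to a trial of an anticoagulant are tied to a looser reference point than the D-dimer, which controls nothing at entry. If a site enrolls and consents a patient a day or more before discharge, as Section 6.2.1 allows, the 72 h limit runs back from that earlier moment and the result is older than 72 h by randomization.

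The patients at issue are those whose platelets, hemoglobin or renal function crossed a limit after the qualifying sample and who had no newer result. Such a patient could be randomized and start 30 days of study drug. The readable encounter lists in Section 6.2.1 schedule no safety laboratory tests after randomization, and Section 5.6.1 lets the investigator stop study drug only once an exclusion is recognized.

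This is a matter of eligibility and participant safety. Any such crossing happens before randomization, so it does not bias the comparison between arms, and it has no bearing on alpha or power.

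**Working it through.** The documents state no figure for the age of these results at randomization, so there is none to reproduce. The upper limit follows by addition.

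**Inputs**

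- Test window before enrollment: 72 h (Protocol 6.2).
- Gap from enrollment to randomization: 0 to about 72 h (Protocol 6.2.1, about Day -3 to Day 0). The 72 h approach window in Protocol 2.2 gives the same outer limit, since enrollment cannot precede approach and randomization is expected on the day of discharge.
- Alternative outer limit for that gap: 48 h (SAP 3.6).

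**Formula**

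Maximum age at randomization = 72 h + time from enrollment to randomization.

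| Enrollment | Calculation | Maximum age as written | Maximum age if dated from randomization | Reduction |
|---|---|---|---|---|
| Day 0 | 72 + 0 | 72 h | 72 h | 0 h |
| Day -1 | 72 + 24 | 96 h | 72 h | 24 h |
| Day -2, or the SAP's 48 h window | 72 + 48 | 120 h | 72 h | 48 h |
| Day -3, or the protocol's 72 h window | 72 + 72 | about 144 h | 72 h | about 72 h |

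The last row is approximate because Section 6.2.1 itself gives Day -3 as approximate. Each figure is a ceiling: it needs the oldest permitted result and the stated enrollment day in the same patient.

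**Whether other text closes the gap**

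- Section 4.1 requires the criteria to be met before both enrollment and randomization, and Section 8.1 screens patients daily. A disqualifying result that is already known therefore bars entry. Neither section orders a new sample.
- Section 5.6.1 covers newly developed or previously unrecognized exclusions and names thrombocytopenia and renal insufficiency as examples. It applies to stopping study drug and sets no limit on the age of a result at randomization.

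What remains is a change that nobody measured between the qualifying sample and randomization.

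**What cannot be computed**

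The documents give neither the share of participants enrolled before Day 0 nor the rate at which patients cross one of the limits over one to three days. The number affected cannot be derived.

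**The case against.** The strongest reply is that enrollment, read in context, means about Day 0. Section 2.2 and SAP Section 3.6 pair final enrollment with randomization and want both as late as possible. Section 4.1 counts follow-up from enrollment, Appendix 4 ties the Day 0 specimens to it, and Section 8.1 randomizes at the baseline visit. The Day -3 label in Section 6.2.1 covers screening and enrollment together, so it need not mean that enrollment is completed that early. On this reading the limit is already 72 h. This has real weight, but it does not settle the matter: Section 6.2.1 lists enrollment with consent as a step ahead of randomization, and a site could reasonably follow it.

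Other points against:

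- **The 144 h figure stacks two maxima, and the 120 h figure uses a SAP window that governs approach, with no rule on tests.** Both are true. They are upper limits, and the usual gap should be shorter.
- **Different reference points can be defended.** Eligibility is judged at the baseline step, whereas D-dimer is an adjustment and subgroup variable. This is why the point is a design choice and not an error. It does not make the older result safer.
- **The clinical effect is slight.** A design with no scheduled safety tests visible during 30 days of treatment changes little when up to three days before discharge are removed. This stands, and it limits the severity.
- **The evidence is incomplete.** The schedule table in Section 6.1 is broken in the available text, and the Manual of Procedures mentioned in Section 12.3 is not available. A repeat-test rule could sit in either, so its absence is established only for the readable text.

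**Conclusion.** The concern holds in its conditional form. If enrollment precedes Day 0, as Section 6.2.1 permits, the hemoglobin, creatinine and platelet results may be more than 72 h old at randomization: about 144 h at most under the protocol's timing, and 120 h at most under the SAP's 48 h window. If enrollment and randomization coincide, the limit is 72 h and nothing is lost.

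The conclusion rests on the Section 6.2.1 reading of enrollment and on there being no repeat-test rule in the parts of the plan that cannot be read. The safety gain from correcting it is small and unquantified. The point is optional, with medium confidence.

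**What to change.** In Section 6.2, date hemoglobin, creatinine and platelet count from randomization in place of study enrollment, keeping the 72 h limit. This caps the age of the results at 72 h however enrollment is understood, uses the same reference point as the study D-dimer, and fits the Section 4.1 requirement that the criteria be met before randomization.

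The cost is one phrase and an occasional repeat inpatient blood sample for an early enrollee with no newer clinical result. That may be a separate draw where the D-dimer came from routine care. The change helps only participants not yet randomized. It does not address changes that arise after randomization.
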